In Canada, little research has been done to evaluate and improve outcomes of children with nephrotic syndrome. It is not known whether variability in treatments affects patient outcomes – addressing this problem is a necessary first step towards improving care and patient experience. A carefully constructed prospective longitudinal cohort with a large and generalizable sample of patients can help us answer this question. Therefore, we have established the first national prospective cohort of children with nephrotic syndrome with the overall goal to provide *best care based on best evidence*.

Over the last 2 years, we received start-up funds from Canadian Institutes of Health Research (CIHR) and other sources to establish this cohort in 13 sites across Canada. We have enrolled 77 patients to date and have provided our preliminary data in this application. The funds received to date are inadequate to reach the sample size needed and to complete the observation period required to address the research questions as proposed *within this* application. We have noted in the proposal and budget, the progress of our ongoing work and where new funds are needed. We have also carefully considered past review committee comments in this re-submission.

We will use the prospective cohort to address the following 2 objectives:

Objective 1

[figure not shown]
- a) To determine the association of steroid dose prescribed (total dose prescribed during observation period divided by total number of days on treatment) and relapse rates (primary outcome defined as total number of relapses divided by total observation time).

Objective 2

- a) to determine the associations between centre-, physician-, patient-level characteristics and i) steroid dose prescribed, and ii) length of steroid treatment for first presentation and subsequent relapses of nephrotic syndrome;

- b) To identify reasons for practice variation in treatments for nephrotic syndrome between and among pediatric nephrology care providers and centres.

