2.2 Steroids are the treatment of choice for first presentation and subsequent relapses of nephrotic syndrome. Clinical response to steroids is the most important predictor of disease course.² Steroid sensitive patients typically respond to treatment with remission of proteinuria within 2 weeks of therapy and maintain normal kidney function. Steroid resistant patients, defined as those who fail to achieve complete remission of proteinuria after 8 weeks of steroid therapy, have a high risk (>50% in 5 years) of kidney failure.^{32,33} Approximately 90% of children with nephrotic syndrome are steroid sensitive, and they will be the focus of our study.^{34,35} Among these patients remission is achievable with steroid treatment; however, relapses are common requiring multiple courses of steroids and steroid sparing immunosuppressive drugs - leading to significant side effects drug toxicity. Of the children who relapse, up to 50% will have frequent relapses (≥ 2 relapses within 6 months of first response or ≥ 4 relapses in any 12 month period) or become steroid dependent (2 consecutive relapses during tapering of steroid therapy, or relapse within 14 days of steroid cessation).^{10,30} Steroid toxicity reported in children with nephrotic syndrome includes growth retardation and obesity,^{7,9,13,36} hypertension,^{11,37} posterior sub-

capsular cataracts,^{6,12} decreased bone mineral density,^{14,15} and impaired glucose tolerance.⁸ Minimizing relapse rates and steroid exposure are the most important goals in caring for these patients and remain the most relevant clinical outcomes.

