2.4 Although a reasonable body of evidence is available to guide practice, practice variation is common in nephrotic syndrome. The available evidence base for treatment of first presentation and relapses of nephrotic syndrome were synthesized and published in several systematic reviews, local guidelines,^{2,40,41} and also in a recent international clinical practice guideline.⁴² Nevertheless, lack of consensus regarding best treatment approaches is a well-known international phenomenon. Variation in care was documented in surveys of American pediatric nephrologists in 2000 and 2009; however, little has been done to address this problem in the United States or elsewhere.^{20,21} We performed a similar survey which was sent to all Canadian pediatric nephrologists (n=58) and achieved a 69% response rate. The results showed significant variation in steroid protocols and also in the choice of steroid sparing drugs and biopsy practices (see manuscript attached, [name] S, *Pediatr Nephrol* 2013). The total duration of steroid therapy ranged from a minimum of 7.5 weeks to a maximum of 26 weeks (median 16 weeks) for first presentation of nephrotic syndrome – likely contributing to considerable variation in cumulative steroid exposure among patients who may otherwise have similar clinical presentations. Sample protocols used by Canadian physicians and centres are shown in Appendix Tables 1a and 1b. The overall impact of this variability in steroid exposure on relapse rates of Canadian children with nephrotic syndrome has not been formally assessed and remains the most important and compelling unanswered question.

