At entry, we will record demographic information (age, gender, ethnicity, family income, parental education, past medical history), height, weight, blood pressure, blood test results (C3, albumin, cholesterol, creatinine), urine protein values by dipstick (routine clinical practice is to use urine albumin dipsticks [Albustix™, Bayer], but urine protein to creatinine ratio will be recorded if available), medical history and details of steroid prescription. For patients entering at first or second relapse, demographic and treatment information regarding first presentation and/or first relapse will be collected using retrospective chart review when available. We will allow for enrollment up to second relapse (lengthening time interval to obtain consent) in order to maximize patient recruitment. Standardized assessments by physicians will be performed at the following study points: study entry, semi-annual study visits, and at study end.

Data for study points will be obtained using one or all of the following methods: chart review, reviewing patient log books of daily home urine protein measurements and steroid dose given, and phone calls to family to confirm details of clinical course (including date of proteinuria remission for each relapse). Logs maintained by patients are part of routine clinical care in nephrotic syndrome; all study patients will be provided with standardized log books for medications and relapse tracking. This schedule and method of assessments for study points were designed to mirror routine clinical care (as reported by most sites) and to maximize feasibility while maintaining ongoing engagement by study patients and physicians.

Defining an episode of treatment: As nephrotic syndrome is a relapsing and remitting disease, a significant portion of the study data will involve documenting treatment for both first presentation and

relapses of nephrotic syndrome (called ‘episodes’ in this study). Detailed steroid prescription information will be recorded at entry, and at the beginning and end of all subsequent episodes.

An **episode** is defined as the time from start of full dose steroid therapy (60 mg/m² or 2mg/kg) to cessation of steroids or re-start of full dose steroids as in steroid dependent patients who relapse while tapering steroids.

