Outcome: The primary outcome of interest is relapse rate (number of relapses/per person unit time). Relapse rate is the most clinically relevant outcome for nephrotic syndrome and the best indicator of morbidity experienced by patients; this outcome definition is consistent with prior literature in this area.⁴⁰

Exposure: The exposure is steroid prescribed per unit time - that is the total dose patients were prescribed as treatment for episodes of proteinuria divided by the sum of duration of 'days on steroids' during observation period. Days on steroids is defined by the sum of the length in days of all episodes (see definition of episode in section 3.1, also graphically represented in Appendix Figure 4) observed. This definition is consistent with measures of steroid exposure used in prior nephrotic syndrome steroid dosing studies conducted in Europe and in a Canadian study of steroid associated osteoporosis in children.^{38,55} Systemic steroid exposure (both oral and intravenous) will be converted into prednisone equivalents (mg/m^2) using standard dose conversion tables and weight based dosing criteria [mg/kg] will be converted to mg/m^2 .

Analysis plan: The unit of analysis is the patient. Given that the main outcome of interest is relapse rate, we will use Poisson regression models with steroid prescribed per unit time as the exposure and relapse rate per unit time as the outcome, adjusting for patient level variables (age, gender, ethnicity, household income, parental education) and episode at entry into study (either first presentation, first relapse or second relapse), and taking into account time at risk. We are not using multi-level (hierarchical) analysis in this objective, as there is no clustering at the patient-level. There is only one measurement per patient, relapse rate adding all episodes experienced by one patient as a count.

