Feasible sample and power considerations: We estimated a feasible sample based on data gathered from 2 sources: an ongoing longitudinal study of children with nephrotic syndrome (INSIGHT study, led by [name]) recruiting a Toronto based cohort,⁵³ and our preliminary data (Appendix Figure 5 for preliminary recruitment rate). Based on the expected consent rate of 72%, and estimated drop out of 10% (due to loss to follow-up or steroid resistance), we estimate that we will be able to enrol and follow, at least, 520 patients over a period of 4.0 years (65 patients every 6 months). In our preliminary work, we have already enrolled 77 patients from 6 sites, thus our total estimated sample is 597 patients.

Although we hypothesize that increasing steroid dose prescribed per unit time will be associated with decreasing relapse rates, no studies to date have reported a specific magnitude of the effect of steroid prescribed per unit time on relapse rates. A systematic review of available clinical trials examining this issue, published in 2007, only reports on risk ratios based on the dichotomous outcome of any relapse at a pre-specified time interval (usually 12 or 24 months).⁴⁰ Our outcome of interest is an actual rate (count of relapses/person years). Hence, a power based, effect size dependent sample size calculation was not performed. At a significance level $\alpha = 0.05$, and under the following assumptions of a mean daily steroid dose of $30.64 \text{ mg}/\text{m}^2$ with a standard deviation (of the dose) of 8.85, a base rate of relapse of 1.68 per person year, average follow up (time at risk of relapse) of 2 years and a conservative correlation (R^2) of the steroid dose with other covariates of 0.2, we would have 90% power to detect an incidence rate

ratio of 0.989 or smaller (i.e. a larger effect size) in a multiple Poisson regression. We are allowing for a 2 tailed test to allow the possibility of the effect being on either side of the null.

3.3 Work Plan for Objective 2

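### The Objective 1 dose exposure is averaged over the same follow-up in which relapses are counted, so relapses partly create it and the planned model can show a dose association when there is none

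*Protocol*

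**What the plan says.** Section 3.2 (Exposure) takes "the total dose patients were prescribed as treatment for episodes of proteinuria divided by the sum of duration of" days on steroids, summed over all episodes observed. The outcome in section 1.0 (Objective 1) is the "primary outcome defined as total number of relapses divided by total observation time". Exposure and outcome share one window, with no lag or landmark.

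Section 3.1 ends an episode at "cessation of steroids or re-start of full dose steroids as in steroid dependent patients who relapse while tapering steroids". Section 2.2 lists relapse during taper among the features of children who "become steroid dependent (2 consecutive relapses during tapering of steroid therapy, or relapse within 14 days of steroid cessation").

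The analysis plan in section 3.2 is a patient-level Poisson regression: "There is only one measurement per patient, relapse rate adding all episodes experienced by one patient as a count". It adjusts for age, gender, ethnicity, household income, parental education and episode at entry, and takes account of time at risk. Section 3.2 hypothesises that a higher dose per unit time goes with fewer relapses (section 3.2, Design). For that model the power paragraph says "we would have 90% power to detect an incidence rate" ratio of 0.989 or smaller. The limitations in section 4.0 mention unmeasured confounders, adherence and changing practice, but not this dependence.

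**The concern.** Dose prescribed because of a relapse is used to explain that relapse. There are two routes.

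1. **Mixing of courses.** If relapse courses have a different mean daily dose from first courses, the average shifts with the relapse count. Lighter relapse courses make frequent relapsers look low-dose, which mimics benefit of a higher dose.
2. **Cut tapers.** A relapse during taper removes that course's remaining low-dose days and raises the average, which mimics harm. This falls most on the children who relapse most.

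Both act after entry, so baseline covariates and entry episode cannot remove them. The bias is nil only if all courses have the same mean daily dose and none is cut short. The two routes can also offset each other, so a null result would be no safer. Section 7.0 presents Objective 1 as the impact of steroid variability on outcomes, and section 6.0 uses the results to draft best-practice approaches.

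**Working it through.** **1. The plan's own benchmark.** Inputs from section 3.2: rate 1.68 per person-year, 2 years, SD of dose 8.85, R² 0.2, two-sided 5%, power 90%. Reading the IRR as per 1 mg/m²/day, b = ln 0.989 = −0.01106. The simple formula is

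N = (1.960 + 1.282)² / [T·λ·b²·SD²·(1 − R²)] = 10.51 / (2 × 1.68 × 0.0001223 × 78.32 × 0.8) = 408.

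The Poisson-regression formula with 1.68 read as the rate at dose zero gives 469, which matches 520 × 0.9 = 468. So 0.989 reproduces and is a fair yardstick. Its mirror image is 1/0.989 = 1.011.

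**2. Route 1 by hand.** Full dose 60 mg/m² is the protocol's. The alternate-day dose of 40 mg/m² (20 per day) and the relapse course are assumed, for illustration only.
- First course, 6 + 6 weeks: (42×60 + 42×20)/84 = 40.
- Relapse course, 2 + 12 weeks: (14×60 + 84×20)/98 = 25.7.
- Exposure with 0, 1 and 3 relapses, no course cut: 40; (3360 + 2520)/182 = 32.3; (3360 + 7560)/378 = 28.9.

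**3. Route 2 by hand.** Use the same 6 + 6 course every time. Cut by a relapse on day 60, the first course averages (2520 + 18×20)/60 = 48. One relapse then gives (2880 + 3360)/(60 + 84) = 43.3, against 40 with none.

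**4. Null simulation, calibrated.** There were 60,000 patients in each of 40 settings, with no dose effect.
- From the protocol: first courses of 4+4 or 6+6 weeks, or a surveyed length that "ranged from a minimum of 7.5 weeks to a maximum of 26 weeks (median 16 weeks"); relapse rate 1.68 per year; exposure SD 8.85.
- Assumed: relapse courses, entry mix, alternate-day dose 40, gamma heterogeneity variance 0.5, and 22–50% of relapses on steroids where cutting is possible.
- Model: Poisson with entry-episode terms. The offset is log follow-up when tapers can be cut and log off-steroid time when they cannot.

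| Situation | IRR per mg/m²/day, planned exposure |
|---|---|
| Relapses can cut tapers | 0.995 to 1.020 |
| Relapses only after steroids stop | 0.988 to 1.008 |
| Equal courses, uncut | 1.000 |
| Equal courses, cut | 1.018 |
| Heterogeneity variance 1.0 | 0.977 to 1.032 |
| No heterogeneity | 0.996 to 1.008 |
| Alternate-day dose 30 | 0.986 to 1.024 |
| Alternate-day dose 60 | 0.991 to 1.016 |

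Six of the 40 settings were as far from 1 as 0.989. In some the two routes cancelled (IRR 1.001). Rejection of the true null at n=597, after scaling for overdispersion, was:
- 26%, 69%, 75% and 100% in four unequal-course settings (the 69% is an uncut setting);
- 99.5% with equal cut courses;
- 2% with equal uncut courses.

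**5. Independent null simulation.** This used 597 patients, 200 replicates, total follow-up as offset and cuttable tapers throughout. Relapses followed a Poisson process independent of dosing. Assumed: taper average 20 mg/m²/day and, in the tail scenarios, 120 days at 5 mg/m²/day.

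| Scenario | IRR (2.5–97.5 percentile) | Robust p<0.05 |
|---|---|---|
| Same course every episode | 1.033 (1.025–1.042) | 100% |
| Shorter relapse courses | 1.015 (1.002–1.028) | 61% |
| Longer relapse tapers | 1.034 (1.009–1.059) | 65% |
| Low-dose tail after second relapse | 0.960 (0.953–0.969) | 100% |
| Same course, heterogeneous rates | 1.088 (1.074–1.104) | 100% |
| Low-dose tail, heterogeneous rates | 0.934 (0.920–0.947) | 100% |

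**6. Exposure fixed beforehand.**
- In step 4, the planned entry-course dose gave 0.9993–1.0009 and a lagged episode model 0.9994–1.0007. Rejection was 2–8% (overdispersion-scaled) and 3–8% (cluster-robust).
- In step 5, the first-course regimen set at entry gave 0.999–1.000 and 4–8% robust rejection.
- Plain Poisson with the entry-course exposure rejected 20–33% when rates were heterogeneous. That is a separate overdispersion problem.

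**The case against.** The strongest reply concerns size. Relapse-course lengths, taper dose, entry mix and heterogeneity are all assumed, and 34 of the 40 calibrated settings lie closer to 1 than 0.989. Where relapses can cut tapers, as the protocol describes, the calibrated range reaches only 0.995 on the benefit side. The 0.988 comes from uncut settings, which use a different offset. A similar re-run gave 0.994 to 1.017 with cutting, and 1 of 15 settings passed the benchmark. The step 4 and step 5 sizes also disagree (1.018 against 1.033 for equal cut courses). Dividing by days on steroids rather than calendar time does remove the most direct coupling.

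Much of this stands: the figures illustrate and are not an estimate of the bias to expect. It does not rescue the analysis. Step 5 keeps the total-time offset and cuttable tapers, and its low-dose-tail scenario still gives 0.960. A further null simulation on those terms ranged from about 0.973 to 1.129, with 15–100% robust rejection, while the entry-course exposure stayed at 0.997–1.004. A bias smaller than 0.989 can still produce frequent false rejection.

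A second reply is that only an association is claimed. The directional hypothesis and the stated use of the results go further than that.

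A third is that the forms may record the course as it ran, not as planned. That is a fair caution about cost, taken up in the fix.

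**Conclusion.** The concern holds, and the Objective 1 exposure is wrong as written. That the exposure depends on the outcome follows from the protocol's definitions of exposure, outcome and episode, and needs no outside figure. Size and direction cannot be fixed from the document because they rest on the assumed course patterns, taper doses and heterogeneity. Under those assumptions the spurious IRR lies on either side of 1, sometimes beyond the 0.989 the study is powered to detect, and sometimes cancels. A positive, null or reversed Objective 1 result therefore could not be read as an association of dose with later relapse. Confidence is high for the structural fault and low for any particular size.

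**What to change.** Define the exposure so that it precedes the relapses it is meant to explain.

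- **Primary.** Use an episode-level recurrent-event model in which the mean daily dose of the course, as planned at the start of episode k, predicts the time to or rate of the next relapse. Use the whole planned course. The starting dose is full dose by definition, and the course as later cut carries the bias back in. Adjust for course type, prior relapse count, entry episode and steroid-sparing agent status at the start of the interval, with a patient random effect or cluster-robust variance.
- **Simpler alternative.** At patient level, use the planned entry-course mean daily dose, count only relapses after entry, and allow for overdispersion. The offset must match the time at risk. Two exploratory uncut runs gave an entry-course IRR of 1.010 and 1.018 under the null, as would be expected if longer courses use up follow-up that a total-time offset still counts as at risk.
- Keep the whole-period average dose as descriptive only.

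**Cost.** This re-specifies the exposure and model and changes no treatment. It should need no new data, because "Detailed steroid prescription information will be recorded at entry, and at the beginning and end of all subsequent episodes". Section 3.1 also says the forms run from start to cessation or restart, so the sponsor should confirm that the intended course is captured at each start. Later changes to a taper would not be reflected, the patient-level version answers a narrower question about the entry course, and confounding by disease severity is reduced but not removed.

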2.0 DISEASE BURDEN AND MANAGEMENT ISSUES

2.1 Childhood nephrotic syndrome is characterized by severe proteinuria, hypoalbuminemia and edema.¹ The incidence rate of nephrotic syndrome is 2 to 7 cases per 100,000 children per year and prevalence is estimated as 16 per 100,000 children.^{1,24-26} In Canada, approximately 150 children will be diagnosed with nephrotic syndrome each year and there are an estimated 1,000 prevalent patients (data collected from participating sites, see attached support letters). Although the cause of this disease is unknown in most children, nephrotic syndrome can occur in association with genetic mutations in the components of the glomerular filtration barrier, comorbid conditions or environmental triggers.¹ Without treatment, children with nephrotic syndrome develop edema-related complications, pleural effusions, severe infections (e.g. peritonitis, pneumonia, sepsis), thromboembolism and eventually, progress to kidney failure or death.²⁷⁻²⁹ Most (70-90%) children with nephrotic syndrome will have a relapsing course of proteinuria (range of 1 to >20 relapses during childhood) leading to significant morbidity.^{10,30} Therefore, nephrotic syndrome is associated with substantial health system costs which include specialist and multi-disciplinary health care team visits, hospital admissions for control of edema, infection or thrombosis and for kidney biopsies.³¹

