Feasible sample and power considerations: For objective 2, there is no knowledge on expected effects from the explanatory variables on the outcome. Therefore, power calculations, which are based on having a specific alternative hypothesis, are not feasible. The analysis to be performed is a mixed effects model with three random effects (physicians within centre, patients within physicians and episodes within patients), for which there is no simple analytic formula to calculate the needed sample size. The innovative method of Monte Carlo simulation based on the number of subjects potentially available still needs to have as input the expected effects from each of the explanatory variables. In the case of this linear mixed model (for primary outcome), the effect of each variable is measured by its coefficient in the regression (for fixed effects) and by the estimated variance of the random effects. As justified in Objective 1, we expect a feasible sample of 597 subjects. Given this estimated enrollment number, and that we will have a total of 8 explanatory variables plus 3 random effects (estimated as parameters in the model), we are complying with the guideline of 10 observations (at the unit of analysis level) per variable.⁶⁰ As the unit of analysis will be the episode and an estimated 70% of patients will have more than one episode during the study, it is important to note that the 597 patients will yield from 597 to 1015 observations (episode at entry plus one additional relapse). This will ensure that estimates of random effects are feasible.

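### Objective 1's stated 90% power at IRR 0.989 holds only if relapse counts have almost no extra-Poisson variation, an assumption the protocol neither states nor tests over a range

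*Protocol*

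**What the plan says.** Protocol section 3.2, Analysis plan, takes the patient as the unit of analysis: "we will use Poisson regression models with steroid prescribed per unit time as the exposure and relapse rate per unit time as the outcome", with patient covariates, episode at entry and time at risk. It declines a multi-level model and explains: "There is only one measurement per patient, relapse rate adding all episodes experienced by one patient as a count". It names no dispersion term, robust variance or negative binomial alternative.

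Section 3.2, Feasible sample and power considerations, reaches 597 children on feasibility grounds. It then states 90% power, two-sided 5% level, for an "ratio of 0.989 or smaller (i.e. a larger effect size) in a multiple Poisson regression". The listed assumptions are a mean daily dose of 30.64 mg/m² with SD 8.85, an R² of 0.2 with the covariates, and "a base rate of relapse of 1.68 per person year, average follow up (time at risk of relapse) of 2 years". No dispersion value is among them. The unit of the IRR is not given, nor whether 1.68 is the rate at dose zero or the mean rate.

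On differences between children, section 2.1 says: "Most (70-90%) children with nephrotic syndrome will have a relapsing course of proteinuria (range of 1 to >20 relapses during childhood"). Section 2.2 says: "Of the children who relapse, up to 50% will have frequent relapses", or become steroid dependent.

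**The concern.** A Poisson model sets the variance of each child's count equal to its mean. If children who share the same covariates still have different underlying relapse rates, the variance exceeds the mean, even with one count per child. The dose coefficient is then less precise than the power statement assumes.

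The 0.989 figure is the protocol's only statement of what Objective 1 can detect, for the primary outcome. It will frame how a null result is read, and the findings are meant to feed best-practice approaches to treatment. If it rests on an unstated assumption with little slack, a null result could be taken as stronger evidence than it is.

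**Working it through.** **Inputs (section 3.2).** n = 597; mean dose 30.64; SD 8.85; R² = 0.2; follow-up T = 2 years; base rate 1.68; two-sided 5%; power 90%. Assumptions made here: the IRR is per 1 mg/m²/day, dose is roughly normal, and φ is the residual variance-to-mean factor. The protocol gives no φ; plain Poisson means φ = 1.

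**Formula.** With b = ln(IRR) and mean rate r:

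SE = √[φ / (n · r · T · SD² · (1 − R²))]; power = Φ(|b|/SE − 1.96).

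At IRR 0.989, b = −0.01106, and SD²(1 − R²) = 78.32 × 0.8 = 62.66.

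- Mean-rate reading: r = 1.68.
- Dose-zero reading: r = 1.68 × exp(30.64b + (8.85b)²/2) = 1.68 × 0.7125 × 1.0048 = 1.203.

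**Reproducing the protocol's figure (φ = 1).**

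- Dose-zero: SE = √[1/(597 × 1.203 × 2 × 62.66)] = 0.00333; |b|/SE = 3.318; power 91.3%; IRR detectable at 90% power 0.9893, which rounds to the stated 0.989.
- Mean-rate: SE = √[1/(597 × 1.68 × 2 × 62.66)] = 0.00282; |b|/SE = 3.921; power 97.5%; detectable IRR 0.9909.

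The stated figure therefore corresponds to φ = 1.

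**How much extra variation it tolerates.** 90% power needs |b|/SE ≥ 1.960 + 1.282 = 3.2415, so the largest φ is the squared ratio:

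- Dose-zero: (3.318/3.2415)² = 1.048.
- Mean-rate: (3.921/3.2415)² = 1.463.

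If the residual variation comes from children's own rates, φ = 1 + CV² × rT. Then:

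- Dose-zero: CV = √(0.048/2.406) = 0.14. With two equal groups the rate ratio is 1.14/0.86, about 1.3.
- Mean-rate: CV = √(0.463/3.36) = 0.37. The rate ratio is 1.37/0.63, about 2.2.

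So 90% fails once one half of the children relapse, after covariates, at more than about 1.3 or 2.2 times the rate of the other half.

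**Power at 0.989 and detectable IRR, n = 597.**

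| φ | Power, mean-rate | Power, dose-zero | Detectable IRR, mean-rate | Detectable IRR, dose-zero |
|---|---|---|---|---|
| 1 | 97.5% | 91% | 0.991 | 0.989 |
| 1.5 | 89% | 77% | 0.989 | 0.986 |
| 2 | 79% | 65% | 0.987 | 0.984 |
| 3 | 62% | 48% | 0.984 | 0.978 |

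The detectable IRR solves |b| = 3.2415 × SE; on the dose-zero reading r falls as the IRR falls. Simulated gamma-Poisson cohorts (4,000 per setting, 2 years each, robust standard errors) gave power at 0.989 of 79% / 65% at φ = 2 and 63% / 47% at φ = 3.

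**Conditional consequence for the test.** If uncorrected model-based standard errors were used, the true size of a 5% test would be 2[1 − Φ(1.96/√φ)]: 11% at φ = 1.5, 17% at 2 and 26% at 3.

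**The case against.** **The figure is correct on its own terms.** It reproduces, and it is offered under listed assumptions in a Poisson regression. The protocol also says: "Hence, a power based, effect size dependent sample size calculation was not performed". The 597 does not rest on it, and 0.989 is not a target effect. This stands: the calculation is not in error. What is missing is the assumption with the least slack.

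**Loss of power at 0.989 may overstate the harm.** Per SD of dose (8.85), the detectable ratio moves from 0.92 / 0.91 at φ = 1 (mean-rate / dose-zero) to 0.89 / 0.86 at φ = 2 and 0.87 / 0.82 at φ = 3. Nothing in the protocol shows that this makes Objective 1 uninformative. This also stands, and it is why the detectable IRR should be restated.

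**Standard errors belong to the SAP.** Poisson regression is compatible with robust or scaled standard errors, and an SAP not shown may specify them. A reader might infer that the planned test has an inflated type I error. The protocol does not support that, because it does not say which standard errors will be used. Correcting them would not rescue the stated power, however: a corrected test has the lower power shown above whenever φ exceeds 1.

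**The one-count sentence is not about dispersion.** A reader might take "There is only one measurement per patient, relapse rate adding all episodes experienced by one patient as a count" as a claim that extra-Poisson variation is absent. It is offered only as the reason for not using a multi-level model. It neither claims nor secures variance equal to mean.

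**The size is unknown.** The spread in sections 2.1 and 2.2 covers the whole disease course and is not adjusted for covariates. It shows that rates differ, not by how much within this study. A reader might go further and use section 3.3, where "an estimated 70% of patients will have more than one episode during the study", to infer that 30% never relapse and that φ is roughly 3 to 6. That 70% feeds a minimum observation count for Objective 2 (597 × 1.7 = 1015), so it cannot be combined with Objective 1's rate to fix φ.

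**Conclusion.** The point holds in a limited form. The 90% power at IRR 0.989 depends on residual variance being close to the mean. At n = 597 it is lost beyond a factor of about 1.05 on the reading that reproduces 0.989, or 1.46 on the more generous one. The protocol's own account of the disease makes some extra-Poisson variation likely, but its size after covariates is not in the document. Factors 1.5 to 3 are therefore an assumed range, and the consequence runs from none to power of 62% / 48%.

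The results assume an IRR per 1 mg/m²/day, n = 597, a common 2-year follow-up and roughly normal dose. They do not show that the protocol's arithmetic is wrong or that the planned test is anti-conservative. The matter should be fixed, with medium confidence in its practical size.

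**What to change.** **Section 3.2, Analysis plan.** Specify negative binomial regression, or Poisson regression with robust or scaled standard errors, keeping the adjustment for time at risk.

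**Section 3.2, power considerations.** State that 0.989 assumes no overdispersion. State the IRR unit, the n used and what the 1.68 base rate refers to. Give the IRR per 1 mg/m²/day detectable at 90% power for residual variance factors 1, 2 and 3: 0.991, 0.987 and 0.984 if 1.68 is the mean rate, or 0.989, 0.984 and 0.978 if it is the rate at dose zero. Only the row for the chosen meaning of 1.68 is needed.

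The 77 children already enrolled can give a rough guide to the factor, no more. Because the factor grows with follow-up, estimate the between-child variance (CV²) in them and convert it as 1 + CV² × mean count at 2 years.

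**Cost.** One line of analysis wording and a short table; no extra patients, data or change to enrolment. The downside is a less favourable stated detectable effect and, where overdispersion is present, wider confidence intervals than uncorrected Poisson errors would give.
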